Placebo is included for scientific validity in a clinical trial needed to answer study questions related to medication efficacy.

f. Definition of treatment failure or participant removal criteria.

There is no clear definition of treatment failure for this study sample of methadone maintained patients since long-term methadone maintenance is standard care for their chronic relapsing disorder. Patients could potentially be dismissed from treatment for violating clinic rules particularly those relating to violence, firearms possession, drug sales or or other unacceptable behavior at the clinic. Participants could be removed from the study if severe or persistent medication side-effects were observed or if new medical conditions developed including pregnancy or concomitant medications were started that made their continued participation unsafe.

g. Description of what happens to participants receiving therapy when study ends or if a participant's participation in the study ends prematurely.

Study participants will continue on usual care methadone maintenance treatment at their normal methadone clinic after the study or in the event of premature withdrawal from the study.

Study Procedures: Urine Testing. Primary outcomes will be based on qualitative (pos/neg) urinalysis testing results using standard detection cut-off values. In order to detect recent use of cocaine, urine samples will be collected three times per week on non-consecutive days throughout the study, usually on Mon, Wed, and Fri. Sample collection will be observed if possible and all samples will additionally be tested for temperature and adulterants. A second sample will be requested if the original sample fails these tampering tests.

Study Procedures: CM Lead-In. Participants will enter the study following an intensive screening during which eligibility is determined, informed consent is signed and baseline assessment is completed. The study itself begins with a 6-week contingency management lead-in during which vouchers can be earned for submission of cocaine negative urine samples under an escalating schedule with reset to the original value in the case of missing or positive urines. A participant who stops cocaine use on the first day of the study and remains continuously cocaine abstinent would earn \$145 by the end of week 6. However, many participants may start earning later than week 1 or experience resets and thus earn less.

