The aim of this study is to evaluate whether bupropion will enhance cocaine abstinence among methadone-maintained patients who are abusing cocaine. This is being evaluated in a double-blind context. Further, based on evidence that individuals with cocaine use disorder typically present to the clinic with a urine sample that is positive for cocaine (which predicts continued use) or negative for cocaine (which predicts abstinence), we had originally proposed to treat those individuals as two separate groups and run 2 parallel studies (presented as Primary Aims 1 and 2), using contingency management as a background platform to support either abstinence or relapse prevention, respectively. Each aim was intended to enroll 100 individuals (N=200) total, to enable equal distribution of bupropion (n=50) and placebo (n=50) within each aim.

Based on unanticipated difficulties with recruitment, we are now collapsing the two parallel studies into the same overarching study, such that Primary Aim 1 will now be examining the effects of bupropion XL vs. placebo on 24-week abstinence outcomes during and after exposure to a behavioral intervention (CM). We are reducing our sample size to 100 individuals, which still preserves the required 50 participants per medication group that was identified in our power analyses as necessary to detect an effect of the medication. This approach will allow us to achieve our primary aim of determining whether bupropion will enhance cocaine abstinence despite challenges with recruitment and will enable this study to still provide clinically important information to advance the treatment of cocaine use disorder.

We are modifying our statistical plan to accommodate this change in sample size. We will retain the original primary outcome measure (biochemically-confirmed abstinence from cocaine), which will be assessed across all participants (independent of abstinence group) in the same statistical model. The endpoint will be binary (abstinent yes or no), and the treatment effect will be assessed using a repeated-measures logistic regression model having two main effects: medication and time, plus their interaction, as

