well as any necessary covariates, including cocaine positive vs negative urine tests prior to random assignment as a covariate. Generalized linear mixed models (GLMM) will be used to analyze repeated measures data, since this technique can include participants with incomplete data without resorting to imputation. This approach has been found to minimize bias and maximize power in cases of incomplete follow-up (see Hedden et al, 2009). Data will then be examined using the nonbinary method described by McCann and Li (2012) in which participants who meet an end of study threshold of success (1 week EOS abstinence) are assigned values indicating their number of beyond threshold weeks of success (in our case 1-24). This distribution will be analyzed as a function of drug condition using a two-sided Vander Waerden two-sample test (Permutt and Berger, 2000).

All other analyses will be conducted in the overarching group that includes those abstinent and actively using at baseline. This approach will allow us to preserve all study Aims with a reduced sample size that will ensure the study can be completed in the time allowed.

The data analysis plan consists of the following:

- 1) Comparison of groups for baseline differences. Participants will be compared as a function of medication group on baseline characteristics to determine whether they are comparable with respect to general demographic features, baseline drug use, and reinforcement measures (drug vs. money relative reinforcing potency scale, Snaith-Hamilton Pleasure scale). Groups will be compared using t tests for continuous measures and chi-square tests for categorical characteristics. If medication groups are found to differ on baseline measures, then these characteristics will be used as covariates in subsequent analyses assessing treatment effect.
 - 2) Primary outcome analyses: (see above)
- 3) Secondary outcome analyses: The main secondary outcome measure will be biochemically-confirmed abstinence from opiates. We hypothesize that participants receiving bupropion will have a higher proportion of opiate abstinent samples as well as for cocaine. Analyses conducted to assess the treatment effect for opiate use will be identical to those used for cocaine use (described above).

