Many participants who are enrolled in MM continue to abuse illicit drugs, and continued cocaine abuse is the targeted behavior of this study. Although there is no specific pharmacological risk of using cocaine and Bupropion concurrently, use of cocaine (or other illicit drugs) while enrolled in MM treatment is strongly discouraged and will be addressed by counselors during the study. Bupropion could affect the rate of cocaine and other drug use and this will be monitored as part of the study. Money or tangible goods earned in the contingency management program could supply funds for drug purchase. This is no different from the danger associated with funds secured in any other fashion. However, the process is self-limiting in contingency management since submission of a positive urine test immediately stops the dispersal of incentive payments.

Removal to controlled environment

Participants may experience a gap in research participation due to a period of non study-related hospitalization or incarceration. These individuals may be able to re-enter the research. However, such events will be handled on an individual basis according to best clinical judgment, and will take into account the safety and tolerability of inducting the participant back onto the study medication, the ability of the participant to resume reasonable compliance with the study requirements, and any marked changes in baseline cocaine use following the incident.

Pregnancy

There is a possibility that female participants may become pregnant while enrolled in the study and taking methadone and bupropion. Methadone is approved for use among pregnant women.while bupropion XL has been assigned to pregnancy category C where potential risks must be balanced by potential benefits in prescribing the medication. Urine pregnancy tests will be administered at 6-week intervals during the study as part of the health assessment. Study participation will be stopped for any woman who becomes pregnant.

Legal risks: Breach of confidentiality

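### After hospitalisation or incarceration, a participant's cocaine use can influence re-entry to the study, so later primary-outcome urines may be missing for reasons tied to the outcome

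*Combined protocol and SAP*

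**What the plan says.** Section 7, under Removal to controlled environment, covers gaps in participation caused by hospitalisation unrelated to the study or by incarceration. Return is possible but not assured: "These individuals may be able to re-enter the research". The decision is discretionary: "such events will be handled on an individual basis according to best clinical judgment". Three considerations are listed. The first is whether restarting study medication would be safe and tolerable. The second is whether the person can again keep to what the study asks. The third is "any marked changes in baseline cocaine use following the incident". No threshold or direction is attached to the third.

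Section 6 keeps urine-confirmed cocaine abstinence as the primary outcome, analysed as a repeated binary measure. Section 4 (Urine Testing) says that "urine samples will be collected three times per week on non-consecutive days throughout the study". Section 4, item g, says that a participant who leaves early continues on usual methadone treatment; it does not mention further study urines.

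For incomplete data, Section 6 relies on a generalised linear mixed model because "this technique can include participants with incomplete data without resorting to imputation". A further analysis counts weeks of success among participants with one week of abstinence at the end of the study. No rule is given there for someone who was not re-admitted.

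**The concern.** Cocaine use after randomisation is what the trial measures, and Section 7 itself says that bupropion could change it. If that use also influences whether a participant comes back into the study, the value of the outcome affects whether later outcomes are observed. The paragraph treats return to the research as one decision, although restarting capsules and giving urine samples are separate matters. At stake are the abstinence rates after the gap, and the comparison of arms if gaps or cocaine use differ by arm.

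**Working it through.** **Step 1. Does the text allow it?** Four statements, taken together:

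- Cocaine use is a listed consideration for re-entering the research, not only for restarting medication (Section 7).
- The paragraph has no limit to the weeks before randomisation.
- Cocaine use by urine test is the primary outcome (Section 6), measured through study urines (Section 4).
- No continued urine collection is described for people not re-admitted (Section 4, item g).

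The first three are on the page. That urine collection ends on refusal is an inference from the fourth.

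**Step 2. Does the analysis protect against it?** A likelihood-based mixed model on available data is valid if missingness depends only on data in the model. Urines before the gap are in the model. Cocaine use judged at the time of return, and not entered as a study urine, is not. No sensitivity analysis for this is stated. In the end-of-study analysis the effect depends on an unstated scoring choice. If people not re-admitted count as failures, refusing a newly abstinent returnee turns a possible success into a failure. If they are left out, refusing a user raises that arm's rate.

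**Step 3. How large could it be?** The plan gives no gap or re-entry rates, so there is no figure of its own to reproduce. The inputs for illustration are:

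- True abstinence *p*: 0.67 on bupropion and 0.43 on placebo. These are one minus the 0.33 and 0.57 cocaine-positive probabilities that Section 3 quotes from an earlier trial of bupropion with contingency management. The plan prints the same group label for both; the second is taken as placebo. They are not stated design inputs.
- Share with a gap *g*: 5% to 20% (assumed).
- Re-entry probability *r1* if abstinent and *r0* if using: from 0.9/0.1 to 0.1/0.9 (assumed).

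Abstinence observed after the gap = *p*(1 − *g* + *g·r1*) / [*p*(1 − *g* + *g·r1*) + (1 − *p*)(1 − *g* + *g·r0*)].

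Worked case, *g* = 20% in both arms, re-entry 0.9/0.1:

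- Bupropion: 0.67 × 0.98 / (0.67 × 0.98 + 0.33 × 0.82) = 0.6566 / 0.9272 = 0.708.
- Placebo: 0.43 × 0.98 / (0.43 × 0.98 + 0.57 × 0.82) = 0.4214 / 0.8888 = 0.474.
- Difference 0.234 against a true 0.240.

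| Gap rate, bupropion / placebo | Re-entry, abstinent / using | Bupropion | Placebo | Difference | Shift (points) |
|---|---|---|---|---|---|
| 20% / 20% | 0.9 / 0.1 | 0.708 | 0.474 | 0.234 | −0.6 |
| 20% / 20% | 0.1 / 0.9 | 0.629 | 0.387 | 0.243 | +0.3 |
| 5% / 15% | 0.9 / 0.5 | 0.674 | 0.445 | 0.229 | −1.1 |
| 5% / 15% | 0.1 / 0.9 | 0.661 | 0.398 | 0.262 | +2.2 |
| 10% / 20% | 0.9 / 0.1 | 0.688 | 0.474 | 0.214 | −2.6 |
| 10% / 20% | 0.1 / 0.9 | 0.651 | 0.387 | 0.264 | +2.4 |
| 10% / 20% | 0.7 / 0.7 | 0.670 | 0.430 | 0.240 | 0.0 |

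Differences are from unrounded values. With equal gap rates, each arm's rate shifts by about 0.5 to 4 points, but the difference moves by under 1. With true abstinence 0.43 in both arms and gaps of 10% / 20%, a zero difference appears as about −2.3 to +2.3 points. When re-entry does not depend on use, the shift is zero.

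**Step 4. Against sampling error.** With 50 per arm, the standard error of the difference is √(0.67 × 0.33/50 + 0.43 × 0.57/50) = √0.009324 = 0.097, or 9.7 points. The largest shift is 2.6 / 9.7 = 0.27 of that.

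This is a simple proportion at one time after the gap, not a mixed-model estimate.

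**The case against.** Several points on the other side are fair.

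- Cocaine use is one of three considerations under clinical judgment, in a section about risk. A marked change might prompt clinical attention without refusal. This stands: the text permits selection on the outcome but does not require it.
- The word *baseline* may point to the lead-in, since Risks Management in the same section calls the 6 weeks before randomisation the baseline phase. A gap there affects who is randomised, not the randomised comparison. This stands in part: the paragraph is not limited to that phase.
- Research and counselling staff are blinded to medication (Section 4, item c). That limits decisions aimed at one arm. It does not prevent selection on cocaine use, which can differ by arm if bupropion changes use.

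A reader might infer that refused participants leave the data set, so that 20/50 = 40.0% abstinent becomes 20/48 = 41.7%, and that the as-randomised comparison is broken. The documents do not support this for the primary analysis. The mixed model keeps each person's earlier urines in the assigned arm, and nothing defines an analysis set by re-entry. What remains is missingness after the gap.

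**Conclusion.** The point holds as a minor one. For randomised participants, the plan lets cocaine use after the incident influence whether later primary-outcome data are collected. It describes no follow-up for those not re-admitted and leaves their scoring open in the end-of-study analysis. The conclusion rests on the inference that study urines stop when re-entry is refused.

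The effect is probably small: under 1 point on the difference between arms with equal gap rates, and about 1 to 2.6 points in either direction with unequal ones, all under assumed gap rates of 5% to 20%. The sign cannot be known, because a marked rise or a marked fall in use could each count against return. The text does not go so far as to make cocaine use the deciding rule for re-entry.

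**What to change.** Separate the two decisions in Section 7. For every randomised participant who returns, resume the scheduled study urines and assessments regardless of cocaine use. Leave the decision about study medication where it is, with medical staff. Record samples due during confinement as missing with that reason, and note the dates of the gap. State in Section 6 how anyone with no end-of-study urines is scored in the end-of-study abstinence analysis.

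The cost is a sentence or two in the protocol, one reason code for missed samples, and a few extra urine visits for participants who may be off study medication.

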Stratification and Random Assignment. A key feature of abstinence incentive programs is that participants tend to clearly dichotomize into responders and non-responders. The former initiate and sustain abstinence early in the program, while non-responders, either never initiate abstinence or do so intermittently or for only short periods of time before relapsing. In this study, participants will be stratified into CM responders versus non-responders based on submission of two consecutive weeks of cocaine-

free urines (6 samples) during study weeks 1- 6. Considerable experience with implementing these types of interventions suggests that there will be close to a 50/50 split between responders and non-responders by the end of the first month of the CM program.

By the end of study week 6, all participants still active in the study (and independent of exactly where they may be in the abstinence-contingent lead-In earnings plan) will be randomly assigned to bupropion vs placebo medication from within the responder vs non-responder strata and introduced to their tailored earnings schedule for the remainder of the study (see graphs below). Those who qualify for relapse prevention by submitting 2 weeks of negative urines will be randomized on the day they submit the 6th negative urine, while those who will clearly not qualify for relapse prevention will be randomized at the start of week 6.

Medication: Bupropion.

[figure not shown]
Commercially available sources of Bupropion XL and Microcrystalline Cellulose (placebo) will be obtained by the BPRU pharmacy. Qualified pharmacy staff will prepare double blind dosages by overencapsulation of bupropion tablets. The inert substance in both active and placebo capsules will be Microcrystalline Cellulose. Active or placebo capsules will be placed in one-week blister pack kits compatible with daily dispensing requirements of the protocol. When a medication order is provided to the pharmacy, the blister packs will be labeled with a subject number and dispensed to the study site. Study medication blister-packs may be dispensed to participants by nursing staff at the methadone clinic dispensary window or by BPRU research staff. Each kit would contain an accountability log for clinic or study staff to document distribution of capsules from the kit to the study participant. Medication will be stored either in a secure vault at the methadone clinic site or in a pharmacy-approved safe within a locked room.

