Medication dispensing will begin in study week 1 at which time all participants will begin receiving double blind capsules containing placebo. The advantage of this "placebo run-in" is that it stabilizes the medication taking regimen early in the study, precludes "placebo effects" at the time of random assignment and allows for a smooth transition into the post-random assignment study period without any change in study procedures. Participants may be randomized and potentially switched to active bupropion after giving their 6th cocaine negative urine following placebo initiation (week 3 randomization at the earliest) or at the start of study week 6 for those who provide urinalysis evidence of continued active drug use. Consistent with clinical practice for those randomized to active bupropion, there will be a brief (3-day) induction period followed by maintenance dosing at 300mg/day Medication dispensing will continue through week 30. Typically, only a one week supply will be given, but additional medication may be dispensed for holidays, weather-related or other emergencies.

Abstinence incentive schedule initially drug-negative.

The schematic below (left panel) depicts total weekly earnings for accelerating and decelerating phases for those who submit 6 or more negative urines during the CM run-in. The gradual escalation of voucher values begun in week 1 continues for a total of 12 weeks, which includes the Lead-in phase. Reset contingencies have been included for the relapse prevention participants to forestall early relapse. Once randomized to this condition, a cocaine positive or missing sample submitted prior to week 26 will result in reset to the \$3 value. Following a reset, the participant will earn \$3 then \$3.50 for the first two cocaine negative samples then will return to the most recently achieved point in their earning schedule (e.g. \$11 per sample) after the third consecutive cocaine negative sample. Extending the earning period from 24 to 26 weeks allows for completion of the entire earning schedule with 2 brief (single urine positive) slips during which an additional total of \$13 could be earned.

Abstinence Reinforcement Schedules

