Neurocognitive assessment. A battery of tasks designed to measure neurocognitive performance has been developed at the BPRU (Mintzer and Stitzer, 2002) and will be adapted for this study. Functions to be tested include psychomotor speed/pattern recognition (e.g. digit symbol substitution), set shifting/conceptual flexibility (e.g.; trail making tests), divided attention, long-term/episodic memory (e.g. recognition and free recall) and short-term/working memory and focused attention (e.g. N-back task). The Conners Continuous Performance Test will also be used to assess performance in areas of inattentiveness, impulsivity, sustained attention, and vigilance (Epstein et al., 2002).

Inclusion/Exclusion Criteria

Inclusion Criteria:

- Over 18 years old
- Enrolled or meets federal requirements for enrollment in methadone maintenance treatment, and willing to visit the clinic daily
- Evidence of current cocaine dependence (DSM-5 criteria, self-report, urine test positive for cocaine during the intake process or by clinical record during the past 3 months).
- · Willingness to swallow a capsule daily
- Willing to provide observed urine samples three times a week and participate in assessment procedures

Exclusion Criteria:

- Any history of epilepsy or seizure, including alcohol-, sedative-, or cocaine-related seizure;
- Any increased risk of seizure such as serious head trauma with a loss of consciousness of more than an hour duration, brain tumor, or other brain pathology increasing risk of seizure.
- · Current eating disorder including anorexia or bulimia
- Current use (last 30 days) of medication that is contraindicated with bupropion or other bupropion products (e.g. antidepressants, antipsychotics, MAO-A inhibitors, theophyllines, systemic steroids, etc)
- Allergy to bupropion or budeprion
- Liver enzymes greater than 3x ULN
- · Uncontrolled diabetes mellitus, or h/o diabetic coma
- Uncontrolled hypertension with BP > 140/90
- Current psychiatric diagnosis: schizophrenia, psychosis, major depression, mania, current suicidal ideation as determined by MINI psychiatric interview, cognitive impairment severe enough to preclude informed consent or valid responses on questionnaires
- Severe renal insufficiency (eGFR < 30 ml/min)
- Pregnancy or current breast feeding,

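### The plan ties no pregnancy test or new-medication review to randomisation or to the first active dose of bupropion

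*Combined protocol and SAP*

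**What the plan says.** The exclusion criteria in section 4 include "Pregnancy or current breast feeding" and "Current use (last 30 days) of medication that is contraindicated with bupropion" products. They are applied before entry: under CM Lead-In, "Participants will enter the study following an intensive screening during which eligibility is determined".

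The first capsules are not active. Under Medication: Bupropion, "Medication dispensing will begin in study week 1 at which time all participants will begin receiving double blind capsules containing placebo". The same section then says "Participants may be randomized and potentially switched to active bupropion after giving their 6th cocaine negative urine following placebo initiation", with week 3 as the earliest time. Stratification and Random Assignment adds that responders "will be randomized on the day they submit the 6th negative urine". Clear non-responders are randomised at the start of week 6.

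After entry, section 7 (Pregnancy) says "Urine pregnancy tests will be administered at 6-week intervals during the study as part of the health assessment". It calls bupropion XL a pregnancy category C drug and stops participation for any woman who becomes pregnant. Risks Management in section 7 provides a periodic review for intercurrent illness and new medications, with six weeks as an example of the interval. The long assessment visits are at weeks 6, 12, 18, 24 and 30 (section 4b).

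Risks Management does contain one check placed before randomisation: alcohol and sedative use is evaluated during the lead-in, and a participant judged unsafe leaves before being randomised. It also times a blood-pressure check and a mood assessment to one to two weeks after study medication starts.

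**The concern.** In a trial that doses from day 1, screening checks stand directly before exposure. Here a placebo lead-in of two to five weeks separates them. Pregnancy and concomitant medication can both change in that time, and nothing in the text requires either to be confirmed before the switch.

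A woman with an unrecognised pregnancy that began in the lead-in, or a participant who has started an excluded drug, could be randomised and given active bupropion with the plan followed to the letter. She or he would then have to be removed after randomisation. A check on the day could find this first. The plan already accepts the principle for alcohol and sedatives, which makes the omission for these two conditions look like an oversight.

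**Working it through.** **Inputs.** Urine samples three times a week, usually Monday, Wednesday and Friday (section 4, Urine Testing). Placebo from week 1; responders randomised on the day of the 6th negative sample, week 3 at the earliest. Long visits at weeks 6, 12, 18, 24 and 30. N = 100 with 50 per medication group (section 6), and a responder split close to 50/50 (section 4).

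**Reproducing the plan's own timing.** Let day 1 be the Monday of week 1. The 6th sample collected after day 1 falls on day 15, the Monday of week 3, which agrees with the stated earliest week. (Counting a day-1 sample would put the 6th on day 12, in week 2, which the plan's wording rules out.)

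**Minimum age of the entry check at randomisation** = randomisation day − 1, because screening comes no later than day 1:

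| Randomised | Day | Minimum age (days) | With an assumed 0–14 days from screening to day 1 |
|---|---|---|---|
| Monday, week 3 | 15 | 15 − 1 = 14 | 14–28 |
| Friday, week 4 | 26 | 26 − 1 = 25 | 25–39 |
| Friday, week 5 | 33 | 33 − 1 = 32 | 32–46 |
| Monday, week 6, if that week's check is not done first | 36 | 36 − 1 = 35 | 35–49 |

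A Wednesday or Friday start changes the weeks 3–5 range from 14–32 to 14–33 days. The time from screening to day 1 is not given; 0–14 days is an assumption.

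**First recheck.** Assume the 6-weekly checks fall at the long visits, so the first is in week 6, days 36–40. It then comes 36 − 15 = 21 to 40 − 15 = 25 days after the earliest randomisation, and 36 − 33 = 3 to 40 − 33 = 7 days after one on day 33. For every responder randomised in weeks 3–5, day 1 to first recheck is 36 − 1 = 35 to 40 − 1 = 39 days.

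**Comparison with the accepted interval.** Later tests are 6 × 7 = 42 days apart. Counted from day 1, both the 14–32 days and the 35–39 days are shorter. The check carried by a day-33 responder passes 42 days only if screening was more than 42 − 32 = 10 days before day 1.

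**Ceiling on numbers.** 100 × 0.5 responders × 0.5 on active drug = 25. This includes men and any responder who qualifies only in week 6. The documents give no count of women who can conceive and no rate of new excluded prescriptions, so the number actually affected cannot be taken further.

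**The case against.** The strongest reply is that the plan's own tolerance is not exceeded. It lets a woman on active bupropion go 42 days between tests, and counted from day 1 an early responder's check is younger than that. This stands: the length of the gap is not a fault.

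Second, a reader might infer that no test or review takes place between entry and the first active dose. The documents do not support that. The 6-week cycle has no stated start, and the medication review gives its interval only as an example, so an earlier check is possible. The weekly assessment list names neither check, but this is weak evidence: the list for the long visits omits them too, although section 7 says both are done. What the text does show is that no such check is tied to randomisation or first dose.

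Third, a reader might hold the 30-day medication exclusion against the plan at randomisation. It is an entry criterion and the plan does not apply it again, so early responders breach no rule.

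Fourth, supervision is close: clinic attendance is expected daily, study contact is three times a week, staff ask open-ended questions, and a known pregnancy or excluded drug leads to removal. This is real cover and it weakens the medication half of the point, since a question on the day also relies on disclosure. It does not answer the pregnancy half, because contact and questions cannot reveal a pregnancy the woman has not recognised.

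**Conclusion.** The point holds as a small, inexpensive safety improvement. The plan sets its exclusions at screening, starts active drug weeks later, and requires no confirmation of pregnancy status or new medications at that moment. The entry check is at least 14 to 32 days old for responders randomised in weeks 3 to 5, and at most about 25 responders would start active bupropion this way.

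The day counts assume Monday visits from day 1, screening no later than day 1, and an entry pregnancy test, which the exclusion implies but the protocol does not name. That the first recheck falls after these randomisations assumes the 6-weekly checks follow the long visits. The ceiling of 25 assumes the plan's near-even responder split and equal allocation. The documents support no claim of bias or lost power, and none is made.

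**What to change.** On randomisation day, before the first randomised capsule and in both arms, run a urine pregnancy test for women who can conceive on the sample already collected for cocaine testing. Ask every participant about new medications since screening. Randomise only those still eligible. For anyone randomised in week 6, do that week's check before randomisation. Leave all later checks as they are, and state when the 6-week cycle starts.

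The cost is one dipstick and one question for each responder randomised in weeks 3 to 5, at a visit already held; for week 6 only the order changes. The blind and the endpoint are untouched. Pregnancies that begin after randomisation would still be covered only by the 6-weekly tests.
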